### 4.4 WITHDRAWAL CRITERIA

Patients can withdraw at any point during the study without being required to provide reason for this.

## 5. ADVERSE EVENTS

### 5.1 DEFINITIONS

**Adverse Event (AE):** any untoward medical occurrence in a patient or clinical study subject.

**Serious Adverse Event (SAE):** any untoward and unexpected medical occurrence or effect that:

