**Requires hospitalisation, or prolongation of existing inpatients' hospitalisation**

**Results in persistent or significant disability or incapacity**

**Is a congenital anomaly or birth defect**

Medical judgement should be exercised in deciding whether an AE is serious in other situations. Important AEs that are not immediately life-threatening or do not result in death or hospitalisation but may jeopardise the subject or may require intervention to prevent one of the other outcomes listed in the definition above, should also be considered serious.

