### 5.2 REPORTING PROCEDURES

All adverse events should be reported. Depending on the nature of the event the reporting procedures below should be followed. Any questions concerning adverse event reporting should be directed to the Chief Investigator in the first instance.

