#### 5.2.2 SERIOUS AEs

An SAE form should be completed and faxed to the Chief Investigator within 24 hours. However, relapse and death due to pre-existing conditions and hospitalisations for elective treatment of a pre-existing condition do not need reporting as SAEs.

All SAEs should be reported to the London-Harrow Regional Ethics Committee where in the opinion of the Chief Investigator, the event was:

- 'related', ie resulted from the administration of any of the research procedures; and
- 'unexpected', ie an event that is not listed in the protocol as an expected occurrence

Reports of related and unexpected SAEs should be submitted within 15 days of the Chief Investigator becoming aware of the event, using the NRES SAE form for non-IMP studies. The Chief Investigator must also notify the Sponsor of all SAEs within 24 hours of becoming aware of these.

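### Section 5.1 makes unexpectedness part of being an SAE, while section 5.2.2 applies it as a later filter on SAEs; a foreseeable serious event can miss both 24-hour notices

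*Protocol*

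**What the plan says.** Section 5.1 gives two definitions. An adverse event is "any untoward medical occurrence in a patient or clinical study subject". A serious adverse event is "any untoward and unexpected medical occurrence or effect that" leads to death, threat to life, hospitalisation, disability or congenital anomaly. The section then adds a judgement clause for important events outside that list: "Medical judgement should be exercised in deciding whether an AE is serious in other situations".

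Section 5.2 opens with a general duty, "All adverse events should be reported", and gives no time limit. Section 5.2.1 asks that non-serious events be recorded, whether or not they were expected.

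Section 5.2.2 sets the timed duties for SAEs:

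- To the Chief Investigator: "An SAE form should be completed and faxed to the Chief Investigator within 24 hours".
- To the Sponsor: the Chief Investigator passes on every SAE within 24 hours of learning of it.
- To the ethics committee, a subset only: "All SAEs should be reported to the London-Harrow Regional Ethics Committee where in the opinion of the Chief Investigator, the event was" both related and unexpected. The second condition is worded "unexpected', ie an event that is not listed in the protocol as an expected occurrence". The timing is "Reports of related and unexpected SAEs should be submitted within 15 days of the Chief Investigator becoming aware of the event".

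**The concern.** Seriousness concerns the outcome of an event. Expectedness concerns whether it was foreseen. Section 5.2.2 keeps the two apart, but section 5.1 merges them by making unexpectedness a condition of being an SAE at all.

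Both 24-hour notices are triggered by SAE status alone, so any word that narrows the SAE definition also narrows them. Healthy volunteers here take five doses of oral penicillin before the study day and one on it, and have a microneedle sensor and a cannula sited. A serious drug reaction or an infection at an insertion site is an event that staff could reasonably call foreseeable. If they then conclude that it is not an SAE, the Chief Investigator and the Sponsor may not hear of it within 24 hours.

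At stake are the timing of safety notices and Sponsor oversight in a study of 10–15 volunteers at one facility. Whether the event is reported at all is not in question, nor are sample size, error rates or analysis.

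**Working it through.** The protocol gives no figure to reproduce. The check sets the provisions side by side.

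**1. Where the word occurs.** *Unexpected* appears three times in section 5: once in 5.1, inside the SAE definition and undefined, and twice in 5.2.2, applied to events already called SAEs and defined once. Section 5.1 does not refer forward to 5.2.2.

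**2. Can both sections be literal?** Under 5.1, every SAE with a listed outcome is unexpected. The expectedness test in 5.2.2 would then remove none of them. That test, and the contrast between SAEs that are related and unexpected (ethics committee) and all SAEs (Sponsor), make sense only if some SAEs are expected. The sections conflict, and 5.1 is the odd one out.

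**3. Order of decisions.** In 5.2.2 the Chief Investigator judges expectedness, and the answer affects only the ethics-committee report. Under 5.1 it must be settled before the event is an SAE, and so before the form is faxed to the Chief Investigator. The test is applied ahead of the person assigned to make it.

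**4. Which procedure covers a foreseeable hospitalisation?** It is not non-serious, so 5.2.1 does not fit. On the literal wording of 5.1 it is not an SAE, so 5.2.2 does not fit. Only the untimed general duty in 5.2 remains. The judgement clause in 5.1 does not clearly bring it back, because that clause is written for events outside the listed outcomes.

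**5. Consequence by reading, for a serious event judged foreseeable.**

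| Meaning in 5.1 | Meaning in 5.2.2 | 24-hour notices at risk | Effect of deletion on ethics-committee reports |
|---|---|---|---|
| As defined in 5.2.2 | As defined | 0 of 2 | None |
| Ordinary sense | Ordinary sense | 2 of 2 | None |
| Ordinary sense | As defined | 2 of 2 | A related event not listed as expected regains the 15-day report that 5.2.2 already asks for |

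The first row gives 0 because the text shown contains no list of expected occurrences, so on that meaning every event is unexpected. In the second row a foreseeable event fails the 5.2.2 filter whether or not 5.1 is changed. In no row does the deletion remove an ethics-committee report. The counts describe what each reading implies; they are not observed frequencies.

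**The case against.** The strongest reply is that the protocol defines the word once, in the same chapter, and that on this definition nothing is lost. Section 5.2 also routes events by their nature, under headings for non-serious and serious events, and most staff would put a volunteer's hospitalisation under the second. Participants must have taken penicillin before without adverse effects, and the protocol nowhere describes a death or hospitalisation as expected.

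Much of this stands. The loss of notices is conditional, and a careful reader of 5.2.2 would probably act correctly. Three supporting arguments should also carry little weight. The protocol states no interval between volunteers and no pause linked to SAE notices, so the benefit of early notice before the next exposure is an inference. The exemption in 5.2.2 for pre-existing conditions covers relapse and death as well as elective admissions, so it is weak evidence of how the SAE definition was meant. The judgement clause in 5.1 says little about the listed outcomes.

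The reply does not remove the contradiction, which exists on either reading. Nor does it justify making a 24-hour safety duty depend on the reader carrying a definition back from a later section. The harmless reading also holds only while no list of expected occurrences is visible. If such a list were added, any serious event on it would fall outside the SAE definition in 5.1 and both notices.

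**Conclusion.** The concern holds. Sections 5.1 and 5.2.2 use expectedness in incompatible ways, and the wording in 5.1 is the one to change. The contradiction is certain from the text; the practical loss is conditional. With the 5.2.2 meaning carried back, 0 of 2 24-hour notices are at risk, assuming the protocol contains no list of expected events beyond the text shown. With the ordinary meaning in 5.1, 2 of 2 are at risk, and the event remains reportable without a deadline. Power, analysis and endpoints are unaffected. This is a limited defect, but it lies in the trigger for urgent safety notices and is worth correcting.

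**What to change.** In section 5.1, delete *and unexpected* from the SAE definition, so that an SAE is defined by its outcome (with the existing judgement clause) and not by whether it was foreseen. Leave *related* and *unexpected* in section 5.2.2 as now worded, as the filter for ethics-committee reports only.

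The cost is two words and at most a few more SAE forms in a study of 10–15 people. No ethics-committee report that 5.2.2 requires is lost, and nothing in dosing, procedures or analysis changes.

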**Results in death**

**Is life-threatening** – *refers to an event in which the subject was at risk of death at the time of the event; it does not refer to an event which hypothetically might have caused death if it were more severe*

**Requires hospitalisation, or prolongation of existing inpatients' hospitalisation**

**Results in persistent or significant disability or incapacity**

**Is a congenital anomaly or birth defect**

Medical judgement should be exercised in deciding whether an AE is serious in other situations. Important AEs that are not immediately life-threatening or do not result in death or hospitalisation but may jeopardise the subject or may require intervention to prevent one of the other outcomes listed in the definition above, should also be considered serious.

### 5.2 REPORTING PROCEDURES

All adverse events should be reported. Depending on the nature of the event the reporting procedures below should be followed. Any questions concerning adverse event reporting should be directed to the Chief Investigator in the first instance.

#### 5.2.1 NON SERIOUS AEs

All such events, whether expected or not, should be recorded.

#### 5.2.2 SERIOUS AEs

An SAE form should be completed and faxed to the Chief Investigator within 24 hours. However, relapse and death due to pre-existing conditions and hospitalisations for elective treatment of a pre-existing condition do not need reporting as SAEs.

All SAEs should be reported to the London-Harrow Regional Ethics Committee where in the opinion of the Chief Investigator, the event was:

- 'related', ie resulted from the administration of any of the research procedures; and
- 'unexpected', ie an event that is not listed in the protocol as an expected occurrence

Reports of related and unexpected SAEs should be submitted within 15 days of the Chief Investigator becoming aware of the event, using the NRES SAE form for non-IMP studies. The Chief Investigator must also notify the Sponsor of all SAEs within 24 hours of becoming aware of these.

**Contact details for reporting SAEs**

**[contact],**

**Urgent attention [name]**

**[contact] (Mon to Fri 09.00 – 17.00)**

**Sponsor office: attn [name]**

**Email: [[contact]](mailto:[contact])**

## 6. ASSESSMENT AND FOLLOW-UP

Patients will not be followed up beyond the five day study period described.

## 7. STATISTICS AND DATA ANALYSIS

**For quantitative evaluation:** The sensor calibration will be undertaken by members of Imperial Biomedical Engineering department who have extensive experience of biosensor development and calibration. Pharmacokinetic analysis will be undertaken by [name] using pmetrics, within R.

**Storage:** Data and all appropriate documentation will be stored for a minimum of 10 years after the completion of the study, including the follow-up period. Participant consent forms will be kept in a locked cabinet within a locked room on the 7th floor of the commonwealth building. Only researchers and those with clearance to perform regulatory audits of research procedures will have access to this

Anonymised data will be stored on an Imperial College networked computer within the firewall. This will be accessible to researchers only.

## 8. REGULATORY ISSUES

### 8.1 ETHICS APPROVAL

The Chief Investigator is obtaining approval from the Research Ethics Committee and HRA. The study will be conducted in accordance with the recommendations for physicians involved in research on human subjects adopted by the 18th World Medical Assembly, Helsinki 1964 and later revisions.

### 8.2 CONSENT

Consent to enter the study must be sought from each participant only after a full explanation has been given, an information leaflet offered and at least 24 hours has been allowed to decide upon participation. Signed participant consent will be obtained. The right of the participant to refuse to participate without giving reasons will be respected. After the participant has entered the study the clinician remains free to give alternative treatment to that specified in the protocol at any stage if he/she feels it is in the participant's best interest, but the reasons for doing so should be recorded. In these cases the participants remain within the study for the purposes of follow-up and data analysis. All participants are free to withdraw at any time from the protocol treatment without giving reasons and without prejudicing further treatment.

### 8.3 CONFIDENTIALITY

Patient Identifiable Data from clinical and laboratory databases will only be accessed within the host NHS Trust firewall after the clinical team user has passed their Lightweight Directory Access Protocol (LDAP) authentication. Anonymised data will be analysed on an Imperial College London networked computer. Any data used for analysis outside of the firewall will be fully anonymised by recording it against the participants unique participation number.

### 8.4 INDEMNITY

Imperial College London holds negligent harm and non-negligent harm insurance policies which apply to this study.

### 8.5 SPONSOR

Imperial College London will act as the main Sponsor for this study. Delegated responsibilities will be assigned to the NHS trusts taking part in this study.

### 8.6 FUNDING

Imperial College Biomedical Research Centre (BRC) (£260,000) and Institut Merieux Research Grants (Euro 100,000) have funded this research project.

### 8.7 AUDITS

The study may be subject to inspection and audit by Imperial College London under their remit as sponsor and other regulatory bodies to ensure adherence to GCP and the NHS Research Governance Framework for Health and Social Care (2nd edition).

## 9. STUDY MANAGEMENT

The Chief Investigator will be responsible for overall study oversight. They will chair a formal project oversight meeting once a quarter. The meeting will act to iteratively monitor project progress against the key deliverables and outcome measures, plan all future steps and identify any potential issues including the creation of intellectual property and the best methods for dissemination and communication of research and product outcomes.

On a day to day basis the project will benefit from management by the Head of Operations within HPRU who is experienced in integrating the workflows of the multi-professional teams from the collaborating Centres.

The study PI (AH) has an established collaboration with parallel managed teams in the fields of healthcare and bio-technology. The project will be subject to the usual management practices within the groups, meaning that updates of progress will be required at work-stream meetings within HPRU and wider work-in-progress meetings at Imperial College London.

## 10. PUBLICATION POLICY

The methods and results from the evaluation of the closed loop system will be presented at national and international conferences to both infection and patient safety specialists who are researchers and decision makers. Targeting of these specific groups in disseminating the research findings will allow not only engaged and productive feedback, but is also likely to generate further questions and raise awareness of the product as a resource for wider adoption. A key emphasis will be placed on highlighting both the barriers and the facilitators towards project completion, and on the impact of the product on antimicrobial prescribing, patient outcomes and antimicrobial resistance. The impact on patient outcomes will focus on both individual level outcomes, but also look at the wider perspective of the impact of the product on the patient pathway.

High impact peer reviewed publications will arise from this research evaluation, enabling wider engagement of researchers and decision makers. Open-access fees have been included in the research costs requested, against four high impact journals to enable the widest possible dissemination of the findings.

